2.4.4.5 Treatment outcome

2.4.4.5.1 Time to platelet count $\geq 150 \times 10^9/L$

Time to platelet count $\geq 150 \times 10^9/L$ will be summarized using Kaplan-Meier (KM) estimates such as the median, 25% percentile and 75% percentile with associated 95% CIs, as well as the number of events and the number of censored observations. The KM estimates will also be presented graphically.

2.4.4.5.2 Duration of Daily PE

The duration of daily PE will be summarized descriptively per recurrence period.

2.4.4.5.3 Hospitalization/Intensive Care Unit

The number of days of hospitalization as well as the number of days intensive care unit will be summarized by recurrence period.

2.4.4.6 Cognitive assessment

Actual and change from screening/baseline RBANS score will be summarized descriptively for the ITO population. There will be a descriptive comparison of RBANS with the reference population.

2.4.4.7 Quality of life

Actual and change from screening/baseline SF-36 at the Q6M follow-up visits will be summarized descriptively for the ITO population. The actual SF-36 at the end of the recurrence follow-up visit will be summarized for the recurrence population at each recurrence episode.

2.4.4.8 Multiplicity issues

There are no multiplicity issues because no formal statistical test will be performed.

2.4.4.9 Additional efficacy analysis

2.4.4.9.1 Subgroup Analysis

The following endpoints will be summarized for participants with ADAMTS13 activity at the end of the previous TTP (end of the treatment period of the last recurrence episode in the ALX0681C301 trial) $< 10\%$ / $\geq 10\%$ on the ITO population. Subgroup analysis will only be conducted for each subgroup category if at least 5 participants are available.

- Incidence of recurrence of aTTP

Furthermore, the same analysis will be performed by number of recurrences in the ALX0681-C301 trial (1 recurrence, more than 1 recurrence).

2.4.5 Analyses of safety data

The summary of safety results will be presented by treatment group. For the ITO population, the treatment groups are:

- Caplacizumab total: Subjects who received caplacizumab during the ALX0681-C301 study (during the double blind or the open-label periods).
- Not treated: Subjects who never received Caplacizumab during the ALX0681-C301 trial

For the recurrence population, adverse events will be presented for:

- Treated with IMP: patients treated with caplacizumab in the ALX0681-C302 study
- Not Treated with IMP: patients not treated with caplacizumab in the ALX0681-C302 study during the trial

General common rules

All safety analyses will be performed on the ITO and recurrence populations as defined in [Section 2.3.2](#), unless otherwise specified, using the following common rules:

- For analysis related to the Q6M FU visits, the baseline value is defined as screening/baseline value visit. For analysis related to the recurrence period, the baseline value is defined as the recurrence visit value and will be calculated for each recurrence period separately
- For assessments with multiple parameters per participant (such as laboratory assessments), baseline will be determined per parameter individually. It is recognized that baseline assessments may thus come from more than one assessment and not just from the “baseline visit” assessment.
- For quantitative safety parameters based on central laboratory/reading measurements, descriptive statistics will be used to summarize results and change from baseline values by visit.
- The analysis of the safety variables will be essentially descriptive, and no systematic testing is planned.

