2.1.4 Safety endpoints

The safety analysis will be based on the reported adverse events and other safety information, such as clinical laboratory data, vital signs and physical examination.

Observation period

The observation period will be divided into 2 non mutually exclusive periods: the on-study period and the recurrence period.

The on-study observation period is defined as the time from informed consent until the end of the study (defined as last protocol planned visit).

The recurrence period is from the start of the recurrence episode, defined as recurrent thrombocytopenia requiring initiation of daily PE, until the last recurrence follow-up visit of that episode. In case of treatment with the IMP, the recurrence period is divided into 2 epochs:

- the **treatment epoch** is defined as the time from the first administration of the IMP to the last administration of the IMP.
- the **residual treatment** epoch is defined as the time from the last administration of the IMP to the last administration of the IMP + 30 days.

The treatment-emergent adverse event (TEAE) period will include both treatment and residual treatment epochs.

In case treatment with the IMP is not initiated during the recurrence episode, there is no subdivision of the recurrence period into the treatment epoch and the residual treatment epoch. The adverse event occurring during that period are not identified as treatment-emergent adverse events.

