2.4.4 Analyses of efficacy endpoints

All efficacy endpoints related to assessments on the Q6M FU visits will be analyzed using the ITO population. Summarization will be conducted on the total study population and by analysis group. For the group-wise analysis, the following groups will be considered:

- caplacizumab-treated: defined as subjects in the ITO population who have been randomized to caplacizumab in study ALX0681-C301, evaluated up to their first recurrence in the ALX0681-C302 trial;
- standard of care-treated, defined as subjects in the ITO population who have been randomized to placebo in study ALX0681-C301, evaluated up to their first recurrence in the ALX0681-C302 trial.

Subjects who had a recurrence during study ALX0681-C301 or between the Final (28 day) FU visit in study ALX0681-C301 and Screening/Baseline in study ALX0681-C302, will not be considered for the group-wise analyses.

All efficacy endpoints related to assessments during the recurrence period will be analyzed using the recurrence population. The effect of retreatment of caplacizumab on these endpoints will be evaluated. For the group-wise analysis the following groups are considered, unless otherwise specified:

- Treated with IMP: defined as subjects in the recurrence population who received caplacizumab in the ALX0681-C302 during a recurrence episode
- Not treated with IMP: defined as subjects in the recurrence population who did not receive caplacizumab in the ALX0681-C302 during a recurrence episode.

Of note, depending on the recurrence episode, the same subject can appear in both analysis groups.

Select sensitivity analyses may be planned to assess the effect of heterogeneity in the timings of the baseline visit between subjects. Unless specified otherwise, no missing data imputation will be applied, and all efficacy endpoints will be analyzed as observed.

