2.4.5.1 Analyses of adverse events

Generalities

The primary focus of adverse event reporting will be on treatment-emergent adverse events. Pretreatment and posttreatment adverse events will be described separately.

If an adverse event date/time of onset (occurrence, worsening, or becoming serious) is incomplete, an imputation algorithm will be used to classify the adverse event as pretreatment,

treatment-emergent, or posttreatment. The algorithm for imputing date/time of onset will be conservative and will classify an adverse event as treatment emergent unless there is definitive information to determine it is pretreatment or posttreatment. Details on classification of adverse events with missing or partial onset dates are provided in [Section 2.5.3](#).

Adverse events (AEs) will be placed into analysis periods according to their start date (time). The AE will only be presented in the analysis period during which it started, ie, period start date (time) \leq AE start date (time) \leq period stop date (time). There will be no imputation of other missing date (time) fields, nor of the missing parts of other partially known date (time) fields. When needed (e.g., an incomplete date (time) leads to a double phase allocation), the following rules will be applied: adverse events will be allocated on all analysis levels (ie, for analysis periods and subperiods, see [Section 2.5.4](#)) according to their start date (time). In case the adverse event (AE) start date(time) is incomplete, the allocation will be done according to the available parts of the AE start date(time) and taking into account the AE end date(time) (ie, the AE start date(time) cannot be later than the AE end date(time)):

- When, due to missing date (part) an allocation needs to be made to an analysis period, the AE will be allocated to the treatment phase and not off-treatment phase (worst-case allocation).
- When an allocation needs to be made to a specific recurrence period, the AE will be allocated to the first recurrence period.
- When an allocation needs to be made within a recurrence period, the event will be allocated to the daily PE subperiod.

Tables on the recurrence population will include only adverse events that occurred during the recurrence period, treatment-emergent (for patients who received the IMP) and non-treatment emergent (for patients who did not received the IMP).

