2.4.5.5.5 Analysis

Immunogenicity will be assessed through summary tables, figures, and listing of individual results by subject. All immunogenicity data related to assessments on the Q6M FU visits will be analyzed using the ITO population on the following analysis groups:

- Caplacizumab total: Subjects who received caplacizumab during the ALX0681-C301 study (during the double blind or the open-label periods).
- Not treated: Subjects who never received Caplacizumab during the ALX0681-C301 trial

All immunogenicity data related to assessments during the recurrence periods will be analyzed using the recurrence population with the following analysis groups:

- Treated with IMP: patients treated with caplacizumab in the ALX0681-C302 study for the specific recurrence episode
- Not Treated with IMP: patients not treated with caplacizumab in the ALX0681-C302 study for a specific recurrence episode

ADA assay results

The number and percentage of subjects per ADA subject category will be summarized.

Incidence of positive ADA samples by visit.

Spaghetti plot of ADA log₁₀ (titer) vs. time. Negative values for ADA (reported as log₁₀ (titer) < 1.98) will be visualized on the graphs as 1.80 (arbitrarily chosen) to allow plotting. The MRD (or sensitivity of the assay) will be visualized as horizontal line at log₁₀ (titer) = 1.98.

mADA assay results

The number and percentage of subjects per mADA subject category will be summarized. This tabulation and analysis will be performed on a subset of the population, consisting of subjects who were classified as ADA positive based on ADA data.

- Each mADA subject category
- Classified as TE ADA within the pre-Ab negative and within the pre-Ab positive population
- Classified as pre-Ab negative, pre-Ab positive, drug-induced TE negative and drug-induced TE positive

Incidence of positive mADA samples by visit.

Spaghetti plot of mADA log₁₀ (titer) vs. time. Negative values for mADA (reported as log₁₀ (titer) < 1.98) will be visualized on the graphs as 1.80 (arbitrarily chosen) to allow plotting. The MRD (or sensitivity of the assay) will be visualized as horizontal line at log₁₀ (titer) = 1.98.

ADA/mADA assay results (overall subject classification)

The number and percentage of subjects will be summarized by group using following categorization.

- Each overall subject category
- Classified as TE ADA within the pre-Ab negative and within the pre-Ab positive population

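### Recurrence-period adverse event groups are set per patient while treatment emergence is set per episode, so the not-treated column can be incomplete

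*SAP*

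**What the plan says.** SAP 2.4.5 gives two groups for AEs in the recurrence population. One is "Treated with IMP: patients treated with caplacizumab in the ALX0681-C302 study", with no mention of an episode. The other is "patients not treated with caplacizumab in the ALX0681-C302 study during the trial".

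SAP 2.1.4 works by episode: "In case treatment with the IMP is not initiated during the recurrence episode, there is no subdivision of the recurrence period" into treatment and residual epochs, and "The adverse event occurring during that period are not identified as treatment-emergent adverse events". Where drug is given, the treatment-emergent period includes a residual part; that "epoch is defined as the time from the last administration of the IMP to the last administration of the IMP + 30 days".

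SAP 2.4.5.1 then restricts the recurrence-population tables to events in the recurrence period, "treatment-emergent (for patients who received the IMP) and non-treatment emergent (for patients who did not received the IMP").

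Two other sections of the SAP group recurrence data by episode. For efficacy, SAP 2.4.4 adds: "Of note, depending on the recurrence episode, the same subject can appear in both analysis groups". For immunogenicity, SAP 2.4.5.5.5 defines the untreated group as "patients not treated with caplacizumab in the ALX0681-C302 study for a specific recurrence episode".

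**The concern.** A patient treated in one C302 episode and not in another belongs, by SAP 2.4.5, to the treated group for the whole trial. AEs in that patient's untreated episode are not treatment-emergent, so the treated column does not admit them. The patient is not in the untreated group, so that column does not admit them either.

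The protocol can produce such patients. Protocol 3.2.3 bars caplacizumab after a severe or serious hypersensitivity reaction to it in C302, and when a patient is pregnant or intends pregnancy. Protocol 3.2.4.2 keeps patients who stop the drug in follow-up. Someone who reacts in one episode and recurs later is therefore followed through an untreated episode, and a patient who is pregnant at one recurrence may be treated at another.

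At stake is the completeness of the only AE summaries that show recurrence periods by C302 treatment.

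**Working it through.** The plan gives no figure to reproduce. The check applies the three rules literally to each type of patient.

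**Inputs**
- Group: per patient, treated if ever given drug in C302 (SAP 2.4.5).
- Treatment emergence: per episode, with a residual window of 30 days after the last dose (SAP 2.1.4).
- Table content: treatment-emergent events for patients given drug, other events for patients not given drug (SAP 2.4.5.1).

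**Rule that follows**
- Treated column: patient ever treated and event treatment-emergent.
- Not-treated column: patient never treated and event not treatment-emergent.

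| Patient | AE in | Column under the literal rules | Column under per-episode groups |
|---|---|---|---|
| Treated only | treated episode | Treated | Treated |
| Untreated only | untreated episode | Not treated | Not treated |
| Treated, then untreated | untreated episode, 200 days after last dose | Neither | Not treated |
| Treated, then untreated | untreated episode, 20 days after last dose | Treated, if the residual window runs into the next episode | Not treated by episode, but still eligible as treatment-emergent |
| Untreated, then treated | untreated episode | Neither | Not treated |

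The 20 and 200 days are illustrative choices on either side of the 30-day limit. In the 20-day row, two clauses of SAP 2.1.4 conflict: the residual window makes the event treatment-emergent, while the untreated-episode rule says it is not. The SAP does not say which prevails. Early recurrence is not far-fetched: Protocol 1.2.4 describes 7 Phase II relapses 4 to 10 days after caplacizumab was stopped.

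**Where else the events appear**
- SAP 2.4.5.1 summarises all AEs for the ITO population, but only over the whole study, and SAP 2.4.5 groups those tables by C301 exposure. They cannot show untreated C302 recurrences.
- SAP 2.4.5.1 lists all AEs and SAEs, and SAP 2.4.5.2 lists AEs leading to death.
- SAP 2.4.5.1 promises a separate description of events before and after treatment, but specifies no recurrence-population table for them.

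**Size, by illustration.** The documents give no counts. Assume u never-treated and m mixed patients, each with one untreated episode. The share of untreated episodes that the not-treated column covers is u / (u + m).

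| u | m = 0 | m = 1 | m = 2 | m = 3 |
|---|---|---|---|---|
| 1 | 1/1 = 100% | 1/2 = 50% | 1/3 = 33.3% | 1/4 = 25% |
| 2 | 2/2 = 100% | 2/3 = 66.7% | 2/4 = 50% | 2/5 = 40% |
| 3 | 3/3 = 100% | 3/4 = 75% | 3/5 = 60% | 3/6 = 50% |

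**Denominators.** SAP 2.4.5.1 takes percentages over the treatment-group population and rates over months observed in the analysis period. It does not say whether the untreated episodes of a treated patient count towards that group's overall recurrence period. If they do, they add person-time that mostly cannot yield treatment-emergent events, and the treated rate falls.

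**The case against.** The strongest reply is that the SAP often writes of patients when it means patients within an episode. Tables 1 and 2 in SAP 2.5.4 are titled by treated and non-treated patients yet define their periods for each recurrence episode, and the efficacy section openly expects a subject in both groups. A programmer might well build the AE tables by episode. This is a fair reason to call the problem one of wording, but the reference to the whole trial in the not-treated definition points the other way, and nothing in SAP 2.4.5 supplies the episode qualifier.

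A reader might infer that every AE in these episodes is lost from the recurrence tables. The documents do not support that. Events inside the 30-day window can remain treatment-emergent, and SAP 2.4.5.1 sends events with unclear dates to the treatment phase. The same section summarises bleeding and thromboembolic events whether or not they are treatment-emergent, and labels the serious-event tables to cover both kinds. The general restriction on recurrence tables pulls against this, so capture of those events is unsettled, neither assured nor excluded.

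A reader might also infer that the events vanish from the report, or that the repeated-use objective is compromised. Neither follows. The events stay in the ITO tables and the listings. Repeated-use safety rests on episodes in which drug was given, and those counts lose no events. The analysis is descriptive, with no systematic testing planned.

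Finally, not every bar to treatment creates a mixed patient. Hypersensitivity in C301 or a missing baseline visit excludes drug throughout C302, so those patients are never treated and are classified correctly.

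**Conclusion.** The inconsistency is real and the rule is wrong as written. In the general recurrence-period AE tables, events in an untreated episode of a patient treated in another C302 episode fall in neither column, apart from those within 30 days of an earlier last dose. The consequence is an incomplete not-treated column and an unclear person-time base for the treated column; it is not a loss of data from the report.

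The size depends on the number of mixed patients, which the documents do not give and which may be zero; the coverage percentages above rest on assumed counts. The conclusion also assumes that the group definitions in SAP 2.4.5 are applied literally. Because the affected column is small and descriptive, this is a modest point, but the correction is cheap and the SAP already contains most of the wording.

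**What to change.** - In SAP 2.4.5, define both recurrence-population groups by episode, using the form in 2.4.5.5.5, and add the note from 2.4.4 that one subject may be in both groups.
- In SAP 2.4.5.1, make the table-content sentence and the heading sentence for the all-AE summaries refer to episodes with and without drug, not to patients.
- In the same section, count percentage denominators and person-months by the same episode-level groups.
- State a rule that places an AE in an untreated episode, starting within 30 days of an earlier episode's last dose, in one column only. Without it, episode-level groups would leave such an event eligible for both.
- State whether the bleeding, thromboembolic and serious-event tables include events that are not treatment-emergent from untreated episodes.

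The cost is a few SAP sentences and minor programming. No new data are needed.

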2.4.5.1 Analyses of adverse events

Generalities

The primary focus of adverse event reporting will be on treatment-emergent adverse events. Pretreatment and posttreatment adverse events will be described separately.

If an adverse event date/time of onset (occurrence, worsening, or becoming serious) is incomplete, an imputation algorithm will be used to classify the adverse event as pretreatment,

treatment-emergent, or posttreatment. The algorithm for imputing date/time of onset will be conservative and will classify an adverse event as treatment emergent unless there is definitive information to determine it is pretreatment or posttreatment. Details on classification of adverse events with missing or partial onset dates are provided in [Section 2.5.3](#).

Adverse events (AEs) will be placed into analysis periods according to their start date (time). The AE will only be presented in the analysis period during which it started, ie, period start date (time) \leq AE start date (time) \leq period stop date (time). There will be no imputation of other missing date (time) fields, nor of the missing parts of other partially known date (time) fields. When needed (e.g., an incomplete date (time) leads to a double phase allocation), the following rules will be applied: adverse events will be allocated on all analysis levels (ie, for analysis periods and subperiods, see [Section 2.5.4](#)) according to their start date (time). In case the adverse event (AE) start date(time) is incomplete, the allocation will be done according to the available parts of the AE start date(time) and taking into account the AE end date(time) (ie, the AE start date(time) cannot be later than the AE end date(time)):

- When, due to missing date (part) an allocation needs to be made to an analysis period, the AE will be allocated to the treatment phase and not off-treatment phase (worst-case allocation).
- When an allocation needs to be made to a specific recurrence period, the AE will be allocated to the first recurrence period.
- When an allocation needs to be made within a recurrence period, the event will be allocated to the daily PE subperiod.

Tables on the recurrence population will include only adverse events that occurred during the recurrence period, treatment-emergent (for patients who received the IMP) and non-treatment emergent (for patients who did not received the IMP).

When cross-tabulating AE PTs versus an AE attribute (e.g., severity), the worst-case is always applied within each analysis period. This means that when a participant has the same AE PT twice in the same analysis period, then the participant is reported only once: with the worst severity. If this happens in two different analysis periods, the participant is reported twice: once in each analysis period.

AE onset day and AE duration are defined as follows:

- AE onset day
 - AE start date – reference date + 1 day (when the AE start date is completely known)
 - Missing (when the AE start date is incomplete or unknown).
 - Two different onset days will be calculated: one with the reference date being the screening/baseline visit; and the other, for adverse events occurring during the recurrence period, with reference date being the recurrence visit.
- AE duration
 - AE stop date – AE start date + 1 day (when both dates are completely known)

- Trial termination date – AE start date + 1 day (when the AE start date is fully known but the AE is not resolved at the end of the trial): in this case the duration will be presented as “>x days” in the listing rather than “x days”
- Missing (when the AE start date is incomplete or unknown, or when the AE has resolved but with an incomplete or unknown end date).

These derived parameters will only be presented in the listings. Note that the start and stop times of the AE are not used.

AE incidence tables will present by SOC and PT, sorted by decreasing frequency of SOC and PTs within SOCs, the number (n) and percentage (%) of participants experiencing an adverse event. The denominator for computation of percentages is the population within each treatment group.

The following analysis periods will be considered for all TEAEs tables on the recurrence population:

- Treatment daily PE period
- Treatment post-daily PE period
- Overall treatment period
- Follow-up period
- Overall recurrence period

The following analysis periods will be considered for AE occurring in the recurrence periods for patients not treated with the IMP:

- Daily PE period
- Post Daily PE period
- Overall recurrence period

The following analysis period will be considered for the adverse events observed during the study for the ITO population:

- Overall study period

Analysis of all adverse events

The following adverse event summaries will be generated by analysis period for the patients not treated in the recurrence population and for the ITO population.

- Overview of adverse events, summarizing number (%) of participants, the number of events, and the incidence per 100 person months, which will be calculated as: $100 \times (\text{Number of participants with AE}) / (\text{Total number of months observed within analysis period, summed for all participants})$ with any
 - Participants with at least one AE
 - Participants with at least one serious AE

- Participants with at least one AE leading to death
- Participants with at least one PE-related AE (only for the recurrence population)
- Participants with at least one serious PE-related AE (only for the recurrence population)
- Participants with at least one bleeding event, i.e. an event documented as event indicating an increased bleeding tendency
- Participants with at least one bleeding event, based on the Standardized MedDRA Query (SMQ) “Haemorrhage” with exclusion of the PT “TTP”
- Participants with at least one thromboembolic event, based on the SMQ “Embolic and thrombotic events” (arterial, venous, and vessel type unspecified and mixed arterial and venous) with exclusion of the PT “TTP”
- All AE by primary SOC and PT, showing the number (%) of participants with at least 1 AE. The number of events and the number and percentage of participants having an event will be presented.
- AEs will be summarized by SOC, PT and severity. This will be done for each analysis period. The number and percentage of participants having an event will be presented for the worst severity reported for each event.

Analysis of all treatment-emergent adverse events

The following treatment-emergent adverse event summaries will be generated by analysis period for the recurrence population.

- Overview of treatment-emergent adverse events, summarizing number (%) of participants, the number of events, and the incidence per 100 person months, which will be calculated as: $100 \times (\text{Number of participants with AE}) / (\text{Total number of months observed within analysis period, summed for all participants})$ with any
 - Participants with at least one TEAE
 - Participants with at least one serious TEAE
 - Participants with at least one TEAE leading to death
 - Participants with at least one TEAE for which the study drug was interrupted
 - Participants with at least one TEAE for which the study drug was withdrawn
 - Participants with at least one TEAE that was considered treatment-related by the investigator
 - Participants with at least one serious TEAE that was considered treatment-related by the investigator
 - Participants with at least one PE-related TEAE
 - Participants with at least one serious PE-related TEAE
 - Participants with at least one bleeding event, i.e. an event documented as event indicating an increased bleeding tendency

- Participants with at least one bleeding event, based on the Standardized MedDRA Query (SMQ) “Haemorrhage” with exclusion of the PT “TTP”
- Participants with at least one thromboembolic event, based on the SMQ “Embolic and thrombotic events” (arterial, venous, and vessel type unspecified and mixed arterial and venous) with exclusion of the PT “TTP”
- Participants with at least one hypersensitivity reaction, based on the SMQs “Hypersensitivity” (Narrow), “Anaphylactic reaction” (Narrow) and “Angioedema” (Narrow)
- Participants with at least one hypersensitivity reaction, based on the SMQs “Hypersensitivity” (Narrow), “Anaphylactic reaction” (Narrow) and “Angioedema” (Narrow), considered treatment-related by the investigator.
- All TEAE by primary SOC and PT, showing the number (%) of participants with at least 1 TEAE. The number of events and the number and percentage of participants having an event will be presented.
- TEAEs will be summarized by SOC, PT and severity. This will be done for each analysis period. The number and percentage of participants having an event will be presented for the worst severity reported for each event.
- TEAEs considered treatment-related by the investigator will be summarized by SOC and PT. This will be done for each analysis period. The number of events and the number and percentage of participants having an event will be presented.

Analysis of all (treatment emergent) serious adverse event(s)

- Serious (TE)AEs and non-serious (TE)AEs will be summarized by SOC and PT. This will be done for each analysis period. The number of events and the number and percentage of participants having an event will be presented.
- Serious (TE)AEs will be summarized by SOC, PT and severity. This will be done for each analysis period. The number and percentage of participants having an event will be presented for the worst severity reported for each event.
- Serious (TE)AEs considered treatment-related by the investigator will be summarized by SOC and PT. This will be done for each analysis period. The number of events and the number and percentage of participants having an event will be presented.

Analysis of all treatment-emergent adverse event(s) leading to treatment discontinuation

- TEAEs leading to discontinuation will be summarized separately and combined by SOC and PT. This will be done for each analysis period. The number of events and the number and percentage of participants having an event will be presented.

Thromboembolic events

- Thromboembolic events (treatment-emergent or not), based on the SMQ “Embolic and thrombotic events” (arterial, venous, and vessel type unspecified and mixed arterial and venous) with exclusion of the PT “TTP”, will be summarized by SOC and PT. This will be

done for each analysis period and population. The number of events and the number and percentage of participants having an event will be presented.

Bleeding events

- Bleeding events and serious bleeding events (treatment-emergent or not) will be summarized by SOC and PT. This will be done for each analysis period. The number of events and the number and percentage of participants having an event will be presented based on eCRF and SMQ.
- Treatment-emergent bleeding events based on SMQ and bleeding events considered treatment-related by the investigator based on eCRF will be summarized by SOC, PT and severity. This will be done for each analysis period. The number of events and the number and percentage of participants having an event will be presented for the worst severity reported for each event based on the eCRF and SMQ separately.

Hypersensitivity reactions

- Hypersensitivity reactions (including anaphylaxis and angioedema) will be summarized by SOC and PT. This will be done for each analysis period. The number of events and the number and percentage of participants having an event will be presented. This analysis will be repeated for hypersensitivity reactions considered treatment-related by the investigator.

Listings

- Listings will be provided for all AE, SAE, TEAE leading to treatment discontinuation, bleeding events, severe/serious hypersensitivity AE.

